5.1 Initial Registration

- _____ a. Patients must have a morphologically confirmed diagnosis of high risk (see Section [4.2c](#)) acute promyelocytic leukemia (APL), based on bone marrow examination performed within 14 days before registration. The WBC confirming high risk must be obtained within 14 days prior to registration.
- _____ b. Patients who are known to be PML- RAR α negative by the RT-PCR assay required in Section [5.1g](#) below are not eligible. (NOTE: If the RT-PCR result is indeterminate, additional blood specimens should be submitted for RT-PCR testing to avoid indeterminate pretreatment results whenever possible; if the RT-PCR result remains indeterminate after the initial and any additional specimens are assayed, the patient will be eligible provided all other eligibility criteria are met. Patients may be registered before the RT-PCR assay result is known, but if the result is negative they must be removed from protocol treatment and treated at the physician's discretion; see Section [7.3d](#).)
- _____ c. Patients must have reached their 18th birthday.
- _____ d. Patients must not have prolonged QTc > 0.47 seconds.
- _____ e. Patients must not have received prior systemic chemotherapy for acute leukemia, with the exception of the ATRA, which may be administered for up to 5 days prior to registration. Administration of hydroxyurea, corticosteroids, or leukapheresis to control high cell counts prior to registration is permitted.
- _____ f. Pretreatment cytogenetics must be performed on all patients. Participation in cytogenetic studies is mandatory for patients affiliated with CALGB or ECOG. Collection of pretreatment specimens must be completed within 14 days prior to registration to **S0535**. Note that there are also additional time points at which specimens are required to be submitted for cytogenetics (see Section [15.2](#)). Collection and submission of required materials must be by one of the following mechanisms:
- SWOG Sites and Other Sites not Affiliated with ECOG or CALGB: Specimens must be submitted to each institution's preferred cytogenetics laboratory (see Section [15.2](#)).
 - ECOG Sites: Baseline karyotypes must be submitted via **E3903**. Register patient to **E3903** PRIOR to registration to **S0535**. The ECOG patient number will be required at the time of **S0535** registration (see Section [15.3](#)).

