7.3 Induction Chemotherapy

AGENT	DOSE	ROUTE	Time	NOTES
ATRA ^ζ	45 mg/m ² /day (in 2 doses, 22.5 mg/m ² every 12 hours)	PO	every 12 hrs, Day 1 to CR *	With food. See Section 7.3a below.
Gemtuzumab Ozogamicin ^Δ	9 mg/m ²	IV infusion over 2 hours	Day 1 only ^π	
Arsenic Trioxide	0.15 mg/kg/d	IV infusion over 2 hours	5 days/wk beginning on Day 10 and continuing until CR ^ψ	

* For maximum of 90 days, unless prohibited by either unacceptable toxicity or progressive disease.

^π G.O. may be delayed until Day 6 pending confirmation of APL diagnosis by FISH/cytogenetics, or RT-PCR. Hydroxyurea may be utilized during this time, up to 24 hours prior to initiation of gemtuzumab ozogamicin.

^ψ For a maximum of 60 days, unless prohibited by either unacceptable toxicity or progressive disease.

^Δ Recommended premedications prior to gemtuzumab: acetaminophen 1 gm orally, diphenhydramine 50 mg IV, and methylprednisolone 125 mg IV.

^ζ Day 1 of treatment will be the first day the patient is treated with ATRA, regardless of patient's registration status.

a. ATRA will be "rounded" up to the nearest 10 mg, divided into 2 daily doses, given orally every 12 hours with food.

b. **ATRA syndrome:** A spectrum of clinical manifestations of a cardiorespiratory distress syndrome has been described, including respiratory distress, hypoxemia, fever, erythematous rash, pulmonary infiltrates, pleural or pericardial effusions, congestive heart failure with impaired myocardial contractility and episodic hypotension. Patients with this syndrome may develop rapidly progressive cardiopulmonary failure.

If this syndrome is suspected, ATRA should be held and dexamethasone 10 mg IV or PO BID will be given for 3 days. ATRA will be resumed once the signs/symptoms of the syndrome have resolved. Patients with persistent signs/symptoms of the ATRA syndrome after 3 days of dexamethasone or who have recurrence of the ATRA syndrome after restarting ATRA should be discussed with the Study Chair.

- c. **Prolonged QT_c:** Prolongation of the QT_c has been reported with the use of arsenic trioxide in association with electrolyte abnormalities. Therefore, any identified electrolyte abnormalities of potassium, calcium, or magnesium should be promptly corrected to within normal limits prior to and during treatment with arsenic trioxide. EKG must be obtained twice weekly during induction therapy and as clinically indicated.

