Hematologic Acute Hemolysis: In the case of acute hemolysis (CTCAE 3.0 Grade ≥ 3), hold treatment until complete resolution, then resume treatment with a 50% dose reduction (0.075 mg/kg/day). No dose adjustment is necessary for pancytopenia of any grade. If toxicity persists for more than 14 days after holding treatment or recurrent acute hemolysis occurs despite dose reduction, then discontinue arsenic trioxide.

Dermatologic Toxicity: In the case of rash (CTCAE 3.0 Grade ≥ 3), hold treatment until clear clinical evidence of improvement to ≤ Grade 1, then resume treatment with a 50% dose reduction (0.075 mg/kg/day). If toxicity persists for more than 14 days after holding treatment or recurrent dermatologic toxicity occurs despite dose reduction, then discontinue As₂O₃.

Nausea/Vomiting: Nausea/vomiting of any grade should be handled with symptomatic treatment with anti-emetics. If CTCAE 3.0 Grade ≥ 3 vomiting occurs despite adequate trial of anti-emetics, then hold treatment until clinical improvement and then resume treatment at full dose. If treatment-refractory

nausea/vomiting recurs, then hold treatment until improvement is \leq Grade 1 and then resume treatment with a 50% dose reduction (0.075 mg/kg/day). If toxicity persists for more than 14 days after holding treatment or recurrent nausea and vomiting occur despite dose reduction and anti-emetics, then discontinue As_2O_3 .

- **Neurologic Toxicity:** In the case of moderate-severe objective sensory loss or paresthesias; motor weakness; clinically evident hearing loss; locomotor ataxia or dysmetria; agitation, confusion, or hallucination then hold treatment until clear clinical evidence of resolution to \leq Grade 1 and then resume treatment with a 50% dose reduction (0.075 mg/kg/day). If toxicity persists for more than 14 days after holding treatment or recurrent moderate-severe neurologic toxicity occurs despite dose reduction, then discontinue As_2O_3 .
- **Cardiac Toxicity:** Guidelines for the management of prolonged QTc interval are as follows:
 - EKG must be obtained twice weekly during induction therapy and as clinically indicated.
 - Measure the QT interval (from the start of the Q wave to the end of the T wave) and the preceding RR interval. The QTc interval will be calculated as the QT interval (msec) divided by the square root of the RR interval (msec).

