 - QTc interval $<$ 500 msec: No specific therapy needed. Continue As_2O_3 . Serum K^+ and Mg^{++} should be monitored and repeated only if low.
 - QTc interval 500-600 msec: Hold As_2O_3 temporarily and replete serum K^+ and Mg^{++} with IV and/or oral K^+ and Mg^{++} to minimum target levels of 4.0 and 2.0 mg/dL, respectively. Resume As_2O_3 on same day if target levels are achieved and re-check prior to next dose.
 - QTc interval $>$ 600 msec: Hold As_2O_3 . Aggressive IV K^+ and Mg^{++} repletion (for adults $MgSO_4$ can be given as 2 g IV, followed by up to 12 g in 6 hours). If the QTc interval falls below 600 msec, the patient can be sent home with additional oral supplements and should return the following day for re-checking prior to further As_2O_3 treatment. If the QTc interval does not fall below 600 msec with this level of repletion, the patient should undergo EKG monitoring by telemetry, preferably in the hospital, along with continued IV K^+ and Mg^{++} .
 - **Other Arsenic Trioxide-Related Toxicity:** If Grade \geq 3, then hold treatment until clear clinical evidence of resolution to \leq Grade 1 and then resume treatment with a 50% dose reduction (0.075 mg/kg/day). If toxicity persists for more than 14 days after holding treatment or recurrent toxicity occurs despite dose reduction, then discontinue As_2O_3 .

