- Cardiotoxicity:** Adequate LV function will be required as described previously. Patients judged not to have adequate LV function should be discussed with the Study Chair.

d. Dose Modifications for Arsenic Trioxide during Consolidation

- See Section [8.3.b](#) above. For patients requiring dose reduction of arsenic trioxide during induction due to toxicity, the starting dose for consolidation should be reduced to the acceptable dose determined during induction. For patients in whom arsenic trioxide was permanently discontinued during induction therapy, arsenic trioxide will be omitted from Consolidation Cycles 1 and 2, and patients will proceed to Consolidation Cycle 3. For patients experiencing toxicity from arsenic trioxide during consolidation (in the absence of previous toxicity during induction), dose adjustment guidelines as stated in Section [8.3b](#) should be followed.

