- ⊖ Pretreatment, during induction (on Day 42, then q 2 wks until CR is met), prior to Consolidation #1, prior to Consolidation #3, prior to Maintenance, then every 3 months during maintenance. Once maintenance is complete, every 3 months for the 1st year, then every 6 months for the 2nd year, then at the end of the 3rd year from registration. Following completion of maintenance, only aspirate is required. Note that the marrow documenting CR may serve as the prior to Consolidation #1 marrow, providing it was performed within 8 weeks prior to Consolidation registration (see Section [5.2](#)).
- Σ See Section [15.0](#).
- % Chest X-Ray should be done pretreatment and as clinically indicated.
- \$ Obtain within 72 hours prior to the day of treatment. To be performed twice per week for the first 2 weeks of induction, prior to consolidation Cycle 3, and thereafter as clinically indicated.
- ψ On Day 42, then every 2 weeks until criteria for CR are met.
- π Every 3 months during maintenance.
- α Every 2 weeks.
- # See Section [7.5c](#).
- † To be performed prior to each cycle of consolidation.
- f ATRA administration is permitted for up to 5 days prior to registration.
- ¶ RT-PCR required prior to Consolidation #3, but not #4.
- ¿ Follow-up cytogenetics and RT-PCR required at relapse only.
- ü Only submitted centrally for patients affiliated with CALGB or ECOG (see Section [7.8a](#)).

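### Section 8.3b puts RR in msec in the QTc formula, so its 500 and 600 msec arsenic hold limits cannot be reached as written

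*Combined protocol and SAP*

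**What the plan says.** Section 8.3b (Dose Modification for Arsenic Trioxide During Induction, Cardiac Toxicity) has sites measure the QT interval and the RR interval before it, and then gives the correction: "The QTc interval will be calculated as the QT interval (msec) divided by the square root of the RR interval (msec").

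Three tiers follow, all labelled in msec:

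- Below the first limit, arsenic continues: "500 msec: No specific therapy needed".
- In the middle tier, "QTc interval 500-600 msec", arsenic is held temporarily while potassium and magnesium are brought to "minimum target levels of 4.0 and 2.0 mg/dL, respectively".
- Above 600 msec, arsenic is held with aggressive intravenous repletion, and with telemetry if the interval stays above 600.

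Three other places bear on the rule:

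- **Eligibility.** Section 5.1d sets a limit in seconds and gives no formula: "Patients must not have prolonged QTc > 0.47 seconds".
- **Consolidation.** For arsenic toxicity that first appears in consolidation, Section 8.4d refers back to the "dose adjustment guidelines as stated in Section" 8.3b.
- **EKG timing.** Sections 7.3c and 8.3b require an EKG twice a week in induction, and the Section 9.0 calendar cell agrees. The calendar footnote is narrower: "To be performed twice per week for the first 2 weeks of induction, prior to consolidation Cycle 3, and thereafter as clinically indicated". Section 7.3 gives arsenic "5 days/wk beginning on Day 10 and continuing until CR".

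No part of the supplied text gives another QTc formula or corrects the RR unit.

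**The concern.** A QT in msec divided by the square root of an RR in msec is not a quantity in msec, yet the result is compared with limits in msec. The formula and the tiers next to it are therefore on different scales. The mismatch runs in the unsafe direction: it makes every QTc look far too short, so the rule says to continue arsenic when it was meant to say hold.

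What is at stake is patient safety during arsenic treatment, not the trial's inference. The protocol itself treats the risk as real. The arsenic adverse event list in Section 3.2 includes QTc prolongation and ventricular arrhythmia, and Sections 7.3c and 7.4c both warn of it. Scheduled EKGs do not protect against the error independently, because the same formula interprets each tracing.

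**Working it through.** The plan contains no worked QTc value to reproduce, so the check is unit arithmetic on the stated formula.

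**Inputs from the protocol.** Literal formula: QT(msec) / sqrt(RR in msec), Section 8.3b. Limits: 500 and 600 msec, Section 8.3b; 0.47 s = 470 msec, Section 5.1d.

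**Comparison formula.** QT(msec) / sqrt(RR in seconds). At RR = 1000 msec (60 beats per minute) the divisor is 1 and QTc equals QT, so the result is in msec and can be set against the tiers.

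**Ratio.** [QT / sqrt(RR/1000)] / [QT / sqrt(RR)] = sqrt(1000) = 31.62, for every QT and every heart rate. This is a scale factor, not a distance from either limit.

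**Where the limits would sit on the literal scale.** 470/31.62 = 14.9; 500/31.62 = 15.8; 600/31.62 = 19.0.

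**Illustrative tracings** (QT and RR values are assumed):

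| QT (msec) | RR (msec) | As written | RR in seconds | Tier with RR in seconds |
|---|---|---|---|---|
| 400 | 1000 | 400/sqrt(1000) = 12.6 | 400/sqrt(1.0) = 400 | continue |
| 400 | 600 | 400/sqrt(600) = 16.3 | 400/sqrt(0.6) = 516 | 500-600, hold |
| 480 | 600 | 480/sqrt(600) = 19.6 | 480/sqrt(0.6) = 620 | above 600, hold |
| 550 | 700 | 550/sqrt(700) = 20.8 | 550/sqrt(0.7) = 657 | above 600, hold |

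As written, all four fall below 500 and arsenic continues.

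**QT needed to reach a literal 500.** 500 × sqrt(600) = 12,247 msec at RR 600, and 500 × sqrt(1000) = 15,811 msec at RR 1000. Neither is possible.

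**Range.** Assume QT from 300 to 650 msec and RR from 500 to 1200 msec.

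- As written, the lowest result is 300/sqrt(1200) = 8.7 and the highest is 650/sqrt(500) = 29.1. If QT must also be shorter than RR, the highest is 25.3.
- With RR in seconds, the same tracings run from 274 to 919 msec, or to 800 msec with QT shorter than RR.
- More generally, if QT does not exceed RR, the literal result cannot exceed sqrt(RR), which is 31.6 at RR 1000 and 44.7 at RR 2000.

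**EKG coverage on the footnote's reading.** The first two weeks are Days 1-14 and arsenic starts on Day 10, so twice-weekly EKGs overlap arsenic only on Days 10-14. The calendar schedules no EKG during Consolidation Cycles 1 and 2, so there the rule acts only on EKGs a site chooses to obtain.

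**Potassium unit (secondary).** A target of 4.0 mg/dL is 40 mg/L, and 40/39.1 = 1.02 mmol/L. The shared unit cannot be meant for potassium; mEq/L is the likely intention.

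**The case against.** The strongest reply is that the slip reveals itself. A normal tracing gives 12.6 beside tiers of 500 and 600, and every EKG in every patient does the same, so the error does not lie hidden until a prolonged interval is missed. A site must also have judged QTc against 0.47 seconds before registration, so it should already hold a value on the right scale before arsenic begins. Sections 7.3c and 7.4c require potassium, calcium and magnesium to be corrected whatever the QTc. QTc prolongation is a listed arsenic event and toxicity is graded under CTCAE, a route that does not cite this formula.

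These points stand as reasons to expect a limited practical effect. They do not make the instruction right: a site has to depart from the written formula to get a usable QTc. Use of machine-reported QTc would avoid the error, but that is an assumption about practice.

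Two further points are fair. That the tiers assume RR in seconds is an inference, since no section states it, although the msec labels and the 0.47-second limit leave little doubt. And the EKG-frequency mismatch is a separate inconsistency: two sections and the calendar cell say twice weekly throughout induction, and only the footnote narrows it. It bears on how much protection the schedule offers, not on whether the formula is wrong.

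**Conclusion.** The concern holds. The QTc formula in Section 8.3b gives values 31.6 times too small for the limits beside it, and no realistic EKG can trigger either hold tier if the text is followed. The factor is exact and needs no clinical assumption. The illustrative tracings and the 8.7 to 29.1 range rest on assumed QT and RR values; they describe the literal formula, not a share of patients or any observed practice.

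This deserves correction as more than a clerical slip, because it is an operative dosing rule for a drug with a recognised QTc risk and it extends into consolidation. The likely harm is limited for the reasons conceded above, and none is alleged. The potassium unit is a minor companion error with little consequence, since normal potassium is required elsewhere. The clinical thresholds themselves are not in question.

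**What to change.** In Section 8.3b, define QTc as QT in msec divided by the square root of RR in seconds, with the result in msec, and leave the 500 and 600 msec cut-offs as they are. The tiers then share a scale with Section 5.1d: QT 470 at RR 1000 msec gives 470 msec, and QT 500 gives 500 msec. In the same block, give the potassium target its own unit (presumably 4.0 mEq/L) and keep mg/dL for magnesium. Section 8.4d needs no edit, because it refers back to 8.3b.

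The cost is two unit corrections, with no effect on data collection, analysis or sample size. The study is closed to accrual, so the correction matters most for any protocol that reuses this arsenic text.

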- d. Patients may be registered on this study and begin induction chemotherapy before the result of the required pretreatment RT-PCR assay for PML-RAR α is available (see Section 5.1b). If the patient is found to be PML-RAR α -negative, then the patient is removed from protocol treatment and should receive appropriate chemotherapy for non-APL acute myeloid leukemia.

7.4 Consolidation Cycles 1 and 2

- a. Patients who achieve A1 bone marrow, B1 peripheral blood, and C1 extramedullary disease status (see Section 10.1) may be eligible for registration to consolidation therapy (see Section 5.2). Consolidation Cycle 1 therapy should be started within 4 weeks and no later than 8 weeks following documentation of CR.

- b. Consolidation Cycles 1 and 2 Treatment Plan

AGENT	DOSE	ROUTE	Time	NOTES
Arsenic Trioxide	0.15 mg/kg/day	IV over 2 hours	5 days/week x 5 weeks	Repeat after 2 weeks rest*

* Consolidation Cycle 2 may be given after 2 weeks of rest following Cycle 1.

- c. **Prolonged QT_c:** Prolongation of the QT_c has been reported with the use of arsenic trioxide in association with electrolyte abnormalities. Therefore, any identified electrolyte abnormalities of potassium, calcium, or magnesium should be promptly corrected to within normal limits prior to and during treatment with arsenic trioxide.
- d. MUGA or echocardiogram must be performed prior to initiation of Consolidation Cycle 3 (see Section 7.5c). If the test has been performed at baseline or any time prior to Consolidation Cycle 3, it does not need to be repeated immediately before Cycle 3.

7.5 Consolidation Cycles 3 and 4

- a. Patients who remain in A1 bone marrow, B1 peripheral blood, and C1 extramedullary disease status (see Section 10.1) may continue consolidation therapy. Consolidation Cycle 3 should be started within 4 weeks following completion of Consolidation Cycle 2 if possible.
- b. Consolidation Cycle 4 should be started no earlier than 2 weeks, and no later than 8 weeks from recovery to B1 peripheral blood status.
- c. MUGA or echocardiogram must be performed prior to initiation of Consolidation Cycle 3. If the test has been performed at baseline or any time prior to Consolidation Cycle 3, it does not need to be repeated immediately before Cycle 3. EKG should be obtained as clinically indicated thereafter.

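### Section 8.3b gives the potassium and magnesium targets one shared unit, mg/dL; for potassium that is 1.02 mEq/L, a floor that cannot bind when arsenic is released after a QTc hold

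*Combined protocol and SAP*

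**What the plan says.** The cardiac-toxicity guidance in Section 8.3b sorts patients on arsenic trioxide into three QTc tiers. The middle one begins "QTc interval 500-600 msec: Hold". In that tier potassium and magnesium are repleted "to minimum target levels of 4.0 and 2.0 mg/dL, respectively", and arsenic may restart "on same day if target levels are achieved and re-check prior to next dose". The tier sets no QTc value for the same-day restart, so the two electrolyte minimums are its only numeric release test. The tiers below 500 msec and above 600 msec give no numeric electrolyte target.

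Other provisions bear on the same decision:

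- Section 7.3c says that "electrolyte abnormalities of potassium, calcium, or magnesium should be promptly corrected to within normal limits prior to and during treatment with arsenic trioxide", and Section 7.4c repeats this for Consolidation Cycles 1 and 2. Neither gives a number or a unit.
- Section 8.4d applies the 8.3b rules to arsenic toxicity in consolidation.
- On how often the QTc is looked at, Section 8.3b states: "EKG must be obtained twice weekly during induction therapy and as clinically indicated". The EKG footnote to the study calendar in Section 9.0 is narrower: "To be performed twice per week for the first 2 weeks of induction, prior to consolidation Cycle 3, and thereafter as clinically indicated". On either wording, no EKG is scheduled during Consolidation Cycles 1 and 2.

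**The concern.** Two ions share one unit, and the unit fits only one of them. With mg/dL applied to both numbers, the potassium minimum is so low that any potassium value meeting Sections 7.3c and 7.4c also meets it. One of the two conditions for restarting arsenic then cannot fail.

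This is a dosing threshold for a drug whose QTc effect the protocol itself links to electrolyte abnormalities (Section 7.3c). The adverse-event list in Section 3.2b includes both QTc prolongation and hypokalemia. For potassium, what the 500-600 msec tier adds numerically to the general normal-limits rule is a stricter minimum, and that is the part the unit removes.

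**Working it through.** **Inputs from the protocol (Section 8.3b).** Potassium minimum 4.0, magnesium minimum 2.0, one stated unit, mg/dL. Both targets are stated rather than derived, so the plan has no calculation to reproduce.

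**Inputs from outside the protocol.** Atomic weights (physical constants): K 39.1, valence 1; Mg 24.3, valence 2. Lower limit of normal serum potassium, an assumption: 3.5 mEq/L, range 3.4-3.6.

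**Formula.** mmol/L = (mg/dL × 10) / atomic weight; mEq/L = mmol/L × valence.

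**Potassium**

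- As written: 4.0 × 10 / 39.1 = 1.02 mmol/L = 1.02 mEq/L.
- If 4.0 mEq/L was meant: 4.0 × 39.1 / 10 = 15.6 mg/dL.
- Ratio: 15.6 / 4.0 = 3.9.

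**Magnesium**

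- As written: 2.0 × 10 / 24.3 = 0.82 mmol/L, or 0.82 × 2 = 1.65 mEq/L before rounding. This is a workable target.

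**Does the potassium floor ever bind?** Serum values converted to the stated unit:

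| Serum K+ (mEq/L) | In mg/dL | Meets 4.0 mg/dL? |
|---|---|---|
| 1.5 | 5.9 | yes |
| 2.0 | 7.8 | yes |
| 2.5 | 9.8 | yes |
| 3.0 | 11.7 | yes |
| 3.5 | 13.7 | yes |

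Every value passes, including values far below the assumed lower limit of normal.

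**Against the normal-limits rule of Sections 7.3c and 7.4c**

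| Assumed lower limit (mEq/L) | Stated floor as share of limit | Gap up to 4.0 mEq/L |
|---|---|---|
| 3.4 | 1.02 / 3.4 = 30% | 0.6 |
| 3.5 | 1.02 / 3.5 = 29% | 0.5 |
| 3.6 | 1.02 / 3.6 = 28% | 0.4 |

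The stated floor sits well below any of these limits, so the normal-limits rule always binds first. The last column is the range in which an intended 4.0 mEq/L floor would have delayed the restart and the literal one does not.

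**Would changing the shared unit to mEq/L work?** Magnesium 2.0 mEq/L = 1.0 mmol/L = 24.3 mg/L = 2.43 mg/dL. That is 0.43 mg/dL, or 0.43 / 2.0 = 21.5%, above the stated minimum. It would repair potassium and alter magnesium.

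**The case against.** The strongest reply is that the sentence can be read another way. The unit may attach only to the last number, leaving potassium without a unit. A clinician would then probably supply mEq/L, and the floor would bind as intended. The rest of Section 8.3b also needs sensible reading: it defines QTc with the RR interval in msec under the square root, so a QT of 500 and an RR of 800 would give 500 / √800 = 17.7, and nobody would ever reach the 500-600 tier. If readers are trusted there, they can be trusted on potassium. Beyond that, Sections 7.3c and 7.4c keep potassium within normal limits, the calendar schedules electrolytes twice weekly in induction and weekly in consolidation, and Sections 7.0 and 8.7 name a contact for dosing questions.

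Much of this stands, and it limits the harm. Most readers would infer mEq/L, and potassium is not left uncontrolled. It is also fair to call this a unit error rather than a failed calculation. But on the second reading potassium has no unit at all, which is still a defect in a dose-release rule. The normal-limits rule does not restore a floor of 4.0 mEq/L. The RR unit is a separate slip and does not excuse this one.

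**Conclusion.** The concern holds. As written, the potassium minimum in the 500-600 msec tier is 1.02 mEq/L, lower by a factor of 3.9 than the 4.0 mEq/L that was probably meant, and it cannot bind beside the normal-limits rule. The numeric part of the same-day release therefore rests on magnesium. The hold, the repletion of both ions, the magnesium minimum and the re-check all work as written.

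On the literal reading, what is lost is a window of about 0.5 mEq/L (0.4-0.6) just above the lower limit of normal. That width rests on an assumed limit of 3.5 mEq/L (3.4-3.6). The intended potassium unit is itself an inference.

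The reach is mainly induction. Section 8.4d carries the rule into Consolidation Cycles 1 and 2, but the tier would arise there only after a clinically indicated EKG. The protocol gives no frequency for a QTc of 500-600 msec, so the number of patients affected cannot be estimated. No endpoint, sample size, error rate or other statistical figure changes. The point should be fixed because it is a cardiac-safety threshold that is wrong as written.

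**What to change.** In the 500-600 msec bullet of Section 8.3b, give each ion its own unit: K+ 4.0 mEq/L and Mg++ 2.0 mg/dL. The sponsor should confirm the potassium figure and, since the text does not settle it independently, that mg/dL was intended for magnesium. Do not simply replace the shared unit with mEq/L, because that changes the magnesium minimum. Section 8.4d refers back to 8.3b and inherits the correction, so no second edit is needed.

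The cost is a one-line protocol correction, with no added procedures, patients or analyses. The protocol is marked closed effective 06/01/2013, so the correction now matters mainly for the accuracy of the text and for any protocol that reuses it.

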8.3 Induction Therapy

a. Dose Modifications for ATRA During Induction

- Commonly observed toxicities with ATRA include hepatotoxicity (increased AST and ALT), neurologic changes (headache or pseudotumor cerebri), mucocutaneous changes (dry skin, peeling of palms and soles) and others including cheilitis, epistaxis, fatigue, musculoskeletal pain, and conjunctivitis. If a patient experiences a Grade 3 toxicity, ATRA will be held until the toxicity has resolved to \leq Grade 1. At that time, restart ATRA at 75% dose. Recurrent episodes of \geq Grade 3 toxicity will result in discontinuation of ATRA until the toxicity resolves to \leq Grade 1; ATRA will then be resumed with an additional 25% dose reduction. Patients requiring dose reductions that would reduce the dose to less than 25% of the starting dose should be removed from ATRA (continue other therapy) for the remainder of the cycle. ATRA may be used again in subsequent cycles if toxicity has resolved to \leq Grade 1.
- The ATRA syndrome should be treated as outlined in Section [7.3b](#).
- If ATRA related Grade \geq 3 toxicity (excluding ATRA syndrome) does not resolve to \leq Grade 1 within 14 days of occurrence, ATRA will be permanently discontinued.

CLOSED EFFECTIVE 06/01/2013

b. Dose Modification for Arsenic Trioxide During Induction

Missed doses due to holidays or dose modifications will not be made up. Modification of the arsenic dose in these cycles should be made as follows:

- Renal Toxicity

Creatinine	Adjust Dose:
≥ 1.5 x baseline but < 3.0 mg/dL	Hold treatment until creatinine < 1.5 x baseline, then resume treatment at full dose.
≥ 3.0 mg/dL or oliguric renal failure	Hold treatment until creatinine < 1.5 x baseline, then resume treatment with a 50% dose reduction (0.075 mg/kg/day)*

* If toxicity persists for more than 14 days or recurrent renal toxicity occurs despite a dose reduction, then discontinue arsenic trioxide.

Hepatotoxicity: Give the following dose, based on lab values obtained within 2 days prior to therapy

AST (SGOT)	Bilirubin	Adjust dose:
> 5-fold increase over ULN	2-3 fold increase over upper limit of normal (ULN) > 3-fold increase over ULN	Hold treatment until bilirubin < 2x ULN, then resume at full dose Hold treatment until AST < 3x ULN or bilirubin < 2x ULN, then resume treatment with a 50% dose reduction (0.075 mg/kg/day)*

* If toxicity persists for more than 14 days or recurrent hepatotoxicity occurs despite a dose reduction, then discontinue arsenic trioxide.

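### Section 8.3b lets arsenic resume the same day at QTc 500-600 msec on potassium and magnesium targets alone, with no repeat EKG and no QTc value for restarting

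*Combined protocol and SAP*

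**What the plan says.** The cardiac part of Section 8.3b (dose modification for arsenic trioxide during induction) sets three QTc bands.

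- **Below 500 msec:** arsenic continues.
- **500-600 msec:** arsenic is held temporarily and potassium and magnesium are repleted "to minimum target levels of 4.0 and 2.0 mg/dL, respectively". Arsenic may then resume "on same day if target levels are achieved and re-check prior to next dose".
- **Above 600 msec:** arsenic is held and repletion is aggressive. "If the QTc interval falls below 600 msec, the patient can be sent home with additional oral supplements", and a re-check the following day must come before further arsenic. If QTc does not fall below 600 msec, the patient goes on telemetry with continued intravenous repletion.

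The same section says how QTc is calculated: QT in msec divided by the square root of RR, also in msec. On routine monitoring it says "EKG must be obtained twice weekly during induction therapy and as clinically indicated". Section 8.4d applies the 8.3b rules to arsenic in Consolidation Cycles 1 and 2.

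**The concern.** A dose hold triggered by a QTc value would normally be lifted by a QTc value. In the 500-600 msec band it is lifted by two electrolyte results. The re-check comes before the following dose, so it does not protect the same-day one. It also names neither the test nor the result that would keep arsenic on hold.

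At stake is the safety of patients who reach 500 msec. The arsenic adverse event list in Section 3.2 counts both QTc prolongation and ventricular arrhythmia among expected events, so the protocol itself recognises the hazard. Section 5.1d also excludes patients whose QTc exceeds 0.47 seconds at entry.

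**Working it through.** The plan states no figure to reproduce. The check sets the rules side by side, with two small calculations.

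**1. What lifts the hold in each band (Section 8.3b)**

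| QTc | Arsenic | Stated condition for restart | QTc value for restart |
|---|---|---|---|
| < 500 msec | continue | not applicable | not applicable |
| 500-600 msec | hold | K and Mg at target, same day | none |
| > 600 msec, falls below 600 | hold | re-check next day | none |
| > 600 msec, stays there | hold, telemetry | none yet | none |

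Take a patient at 590 msec whose potassium and magnesium reach target. The restart condition is met that day whether or not QTc has moved. The excess over the continue limit can be at most 600 - 500 = 100 msec.

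Now take a patient first seen above 600 msec who is at 590 msec the next day. The > 600 bullet says only that a re-check comes first. The one band that then describes this patient is 500-600 msec, which leads to the same electrolyte-only restart. That routing is an inference, but the text offers no other.

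**2. Whether another section supplies a QTc value**

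- Sections 7.3c and 7.4c require potassium, calcium and magnesium to be corrected before and during arsenic. They give no QTc criterion. They do mean that calcium is not a gap.
- The catch-all arsenic toxicity rule at the end of 8.3b is for other toxicities, and QTc has its own guideline. If applied to QTc, its hold to Grade 1 or less and its half-dose restart would conflict with the same-day restart.
- Section 7.11d refers to unacceptable toxicity as defined in Section 8.0, which defines none for QTc.
- Sections 7.0 and 8.7 offer Study Chair contact but state no value.
- Routine EKGs are not tied to restarting. Section 8.3b has them twice weekly in induction. The EKG footnote in Section 9.0 reads "To be performed twice per week for the first 2 weeks of induction, prior to consolidation Cycle 3, and thereafter as clinically indicated", while arsenic runs "5 days/wk beginning on Day 10 and continuing until CR". The calendar grid shows twice weekly for the induction column and no EKG entry for Consolidation 1-2. On any reading, none of these EKGs has to precede a same-day restart.

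**3. The QTc formula**

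Illustrative inputs (assumed): QT = 450 msec, RR = 800 msec = 0.8 s.

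- As printed: 450 / √800 = 450 / 28.28 = 15.9.
- With RR in seconds: 450 / √0.8 = 450 / 0.894 = 503 msec.

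At RR = 800, the printed formula would need a QT of 500 × 28.28 = 14,140 msec to reach 500. Read literally, neither 500 nor 600 can be reached, and any restart gate at 500 would always be met. Sites presumably use seconds, but a QTc gate needs the formula to be right.

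**4. The potassium unit**

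Both electrolyte targets are printed in mg/dL. For potassium, mEq/L is evidently meant.

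**The case against.** The best defence is that restarting on electrolytes follows the protocol's rationale: Sections 7.3c and 7.4c describe QTc prolongation in association with electrolyte abnormalities. The re-check also sits under guidelines for prolonged QTc, so it can naturally be read to include an EKG, and EKGs are required as clinically indicated. On that reading the unguarded exposure is one dose with electrolytes corrected. The bullet also does not expressly clear a patient whose electrolytes were at target from the start. This narrows the exposure but does not close the gap. The first dose still needs no QTc value, and even a re-check that includes an EKG has no result attached to it.

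Section 3.2 also refers sites to the arsenic package insert. Its content is not in the documents, so whether it fills the gap cannot be checked.

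A reader might infer three stronger points that the documents do not support.

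- *That nothing covers QTc that stays above 600 msec.* Section 8.3b keeps arsenic on hold there with telemetry and continued repletion, and requires a next-day re-check once QTc falls.
- *That the lack of a reduction or stopping rule for persistent or recurrent prolongation is an error.* Other headings do have one; for hemolysis it reads "If toxicity persists for more than 14 days after holding treatment or recurrent acute hemolysis occurs despite dose reduction, then discontinue arsenic trioxide". But the lower renal and hepatic tiers also resume at full dose without one, and nothing in the documents supports the 50% and 14-day values for QTc specifically.
- *That EKG or dose counts measure the problem.* They describe routine surveillance, not restart after a hold. The induction dose maximum is itself unsettled: the Section 7.3 table limits arsenic to 60 days, while 7.8a allows up to 90.

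**Conclusion.** The point holds as a patient-safety gap in the wording. Section 8.3b permits a same-day arsenic dose at a QTc of up to 600 msec, at most 100 msec above the protocol's limit for continuing, on electrolyte results alone. The > 600 msec band is better guarded but also lacks a restart value and leads into the same rule.

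Only patients who reach 500 msec are affected. The documents give no rate for that, so no patient count is stated. The conclusion assumes that the bullets are followed as written, that QTc is calculated with RR in seconds, and that the package insert adds no binding restart value.

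Nothing here touches sample size, error rates or the primary analysis. The protocol is marked closed to accrual effective 06/01/2013, so the correction matters mainly if the regimen text is reused in the Phase III study that Section 11.1 contemplates.

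**What to change.** 1. **500-600 msec bullet.** Replace with: *Hold As2O3; replete to K ≥ 4.0 mEq/L and Mg ≥ 2.0 mg/dL; repeat the EKG; restart As2O3 only once QTc is < 500 msec; repeat EKG and electrolytes ahead of the following dose.*
2. **> 600 msec bullet.** Add: *No further As2O3 until QTc is < 500 msec.*
3. **QTc formula.** Change it to QT in msec divided by the square root of RR in seconds.

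The 500 msec value is the protocol's own limit for continuing arsenic. Using it as the gate for restarting is a clinical choice that the study team should confirm.

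The cost is one extra EKG before restarting in patients who reach 500 msec, and some arsenic doses held longer than now. Those doses are lost, since Section 8.3b states "Missed doses due to holidays or dose modifications will not be made up". A dose-reduction or stopping rule for QTc that persists or recurs, such as the 50% and 14-day rule used elsewhere in 8.3b, is an option for the study team and not part of this change.
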